## **Storage**

Alisertib (MLN8237-004) enteric-coated tablets are packaged in HDPE bottles with rayon coil, induction seal, desiccant packs, and polypropylene child-resistant cap and stored at USP-controlled room temperature (20°C to 25°C) with excursions permitted from 15°C to 30°C.

## Handling

Alisertib (MLN8237-004) drug product is a cytotoxic anticancer drug. As with other potentially toxic compounds, caution should be exercised when handling the 3 dosage forms of MLN8237-004 (capsules, tablets, and oral solution). Refer to published guidelines regarding the proper handling and disposal of anticancer agents.[1, 2]

## 10.2 Idarubicin

**Desription:** (Idarubicin® package insert): Idarubicin HCl Injection contains idarubicin hydrochloride and is a sterile, semi-synthetic, preservative-free solution antineoplastic anthracycline for intravenous use. Chemically, idarubicin hydrochloride is (1S,3S)-3-Acetyl-1,2,3,4,6,11-hexahydro-3,5,12-trihydroxy-6,11-dioxo-1-naphthacenyl-3-amino-2,3,6-trideoxy- $\alpha$ -L-lyxo-hexopyranoside, hydrochloride.

**Molecular weight:** 533.95

Molecular formula: C26H27NO9•HCl

Idarubicin HCl Injection is a sterile, red-orange, isotonic parenteral preservative-free solution, available in 5 mL (5 mg), 10 mL (10 mg) and 20 mL (20 mg) single-use-only vials. Each mL contains idarubicin HCl 1 mg and the following inactive ingredients: glycerin 25 mg and water for injection q.s. Hydrochloric acid is used to adjust the pH to a target of 3.5.

**Warnings:** Idarubicin is intended for administration under the supervision of a physician who is experienced in leukemia chemotherapy. Idarubicin is a potent bone marrow suppressant. Idarubicin should not be given to patients with pre-existing bone marrow suppression induced by previous drug therapy or radiotherapy unless the benefit warrants the risk.

Severe myelosuppression will occur in all patients given a therapeutic dose of this agent for induction, consolidation or maintenance. Careful hematologic monitoring is required. Deaths due to infection and/or bleeding have been reported during the period of severe myelosuppression. Facilities with laboratory and supportive resources adequate to monitor drug tolerability and protect and maintain a patient compromised by drug toxicity should be available. It must be possible to treat rapidly and completely a severe hemorrhagic condition and/or a severe infection.

Pre-existing heart disease and previous therapy with anthracyclines at high cumulative doses or other potentially cardiotoxic agents are co-factors for increased risk of idarubicin-induced cardiac toxicity and the benefit to risk ratio of idarubicin therapy in such patients should be weighed before starting treatment with idarubicin. Myocardial toxicity as manifested by potentially fatal congestive heart failure, acute lifethreatening arrhythmias or other cardiomyopathies may occur following therapy with idarubicin. Appropriate therapeutic measures for the management of congestive heart failure and/or arrhythmias are indicated. Cardiac function should be carefully monitored during treatment in order to minimize the risk of cardiac toxicity of the type described for other anthracycline compounds. The risk of such myocardial toxicity may be higher following concomitant or previous radiation to the mediastinal-pericardial area or in patients with anemia, bone marrow depression, infections, leukemic pericarditis and/or myocarditis. While there are no reliable means for predicting congestive heart failure, cardiomyopathy induced by anthracyclines is usually associated with a decrease of the left ventricular ejection fraction (LVEF) from pretreatment baseline values.

Since hepatic and/or renal function impairment can affect the disposition of idarubicin, liver and kidney function should be evaluated with conventional clinical laboratory tests (using serum bilirubin and serum creatinine as indicators) prior to and during treatment.

# Please refer to the product's package insert for full prescribing and toxicity information.

## 10.3 Cytarabine (Cytosine Arabinoside) (Ara-C)

**Description:** (Cytarabine® package insert) Cytarabine for Injection, commonly known as ara-C, an antineoplastic, is a sterile lyophilized material for reconstitution and intravenous, intrathecal or subcutaneous administration. It is available in multi-dose vials containing 100 mg, 500 mg, 1 g or 2 g sterile cytarabine. The pH of Cytarabine for Injection, is adjusted, when necessary, with hydrochloric acid and/or sodium hydroxide. Cytarabine is chemically 4-amino-1-β-D-arabinofuranosyl-2(1H)-pyrimidinone.

Molecular weight: 243.22

Molecular formula: C9H13N3O5

Cytarabine is an odorless, white to off-white, crystalline powder which is freely soluble in water and slightly soluble in alcohol and in chloroform.

Protocol Version Date: 5/18/2017

**Warnings:** For induction therapy, patients should be treated in a facility with laboratory and supportive resources sufficient to monitor drug tolerance and protect and maintain a patient compromised by drug toxicity. The main toxic effect of Cytarabine at doses used during induction is bone marrow suppression with leukopenia, thrombocytopenia and anemia. Less serious toxicity includes nausea, vomiting, diarrhea and abdominal pain, oral ulceration, and hepatic dysfunction. The physician must judge possible benefit to the patient against known toxic effects of this drug in considering the advisability of therapy with Cytarabine for Injection.

## Please refer to the product's package insert for full prescribing and toxicity information.

The investigator, or a responsible party designated by the investigator, must maintain a careful record of the inventory and disposition of the agent using the NCI Drug Accountability Record or another comparable drug accountability form. (See the CTEP website at http://ctep.cancer.gov/protocolDevelopment for the "Policy and Guidelines for Accountability and Storage of Investigational Agents" or to obtain a copy of the drug accountability form.)

## 11. BIOMARKER, CORRELATIVE, AND SPECIAL STUDIES

## 11.1 Laboratory Correlative Studies

Bone marrow aspirate samples will be obtained prior to treatment, at mid-treatment assessment (range day 13-16), and at count recovery (day 42 or day 63 if 5+2 re-induction was given), or according to the investigator's discretion, whichever occurs first, , as well as at any time of suspected relapse. Additionally, although not mandated, if patients agree to a skin biopsy, a single 6mm punch biopsy will be performed concurrently during the bone marrow aspiration procedure on day 14 (window day 13-16). The punch biopsy will be collected in a specimen cup containing saline (NOT formalin).

The study will require the following volumes of aspirated bone marrow in purple top tubes (if inaspirable, peripheral blood in purple top tubes may be substituted):

[figure not shown]
- Pre-treatment: Bone marrow aspirate (5-10 mL) [or Blood (20 mL)]
- Day 14 (Range days 13-16): Bone marrow aspirate (5-10 mL) [or Blood (20 mL)]; skin biopsy (6mm punch)- optional
- Count recovery or at Day 42 (Range days 35-45) or day 63 if 5+2 given (Range days 55-65)): Bone marrow aspirate (5-10) mL [or Blood (20 mL)]
- In the event of suspected/confirmed relapse: Bone marrow aspirate (5-10 mL) [or Blood (20 mL)]

All specimens should be maintained at room temperature and delivered within 1 day to the processing laboratories. Specimens may be shipped via FedEx priority overnight Monday through

Thursday (excluding holidays). For after hours/evening collections, specimens may be maintained at room temperature and shipped within 4 days of collection. Specimens should be labeled with study 15-334, pt initials, pt study ID number, date and time collection, specimen type: blood, marrow, skin, and must be accompanied by the appropriate requisition form. Bone marrow and/or blood specimens should be delivered to:

Skin biopsies should be delivered to:

We will perform gene panel sequencing ("Rapid Heme Panel") on bone marrow aspirate samples (or peripheral blood) collected at study enrollment, mid-treatment, count recovery, and at relapse/suspicion of relapse. In selected cases, remaining DNA from bone marrow (or peripheral blood) and skin biopsies will be subjected to broader sequence analysis (whole exome or genome). These exploratory analyses will be performed with several hypotheses in mind. First, we will evaluate whether a specific mutational profile is associated with treatment response. Second, we will determine whether there is selective sensitivity to therapy among specific founding clones and/or subclones. Third, we will investigate somatic mutation patterns that are associated with disease progression. Additional laboratory studies will be performed to characterize the functional consequences of aurora kinase inhibition on leukemic blasts during treatment.

## 12. STUDY CALENDAR

Baseline evaluations are to be conducted within 14 days prior to start of protocol therapy.

Assessments must be performed prior to administration of any study agent.

Of note, the cycle 1, Day 1 labs in Calendar below do not need to be reassessed for purposes for study enrollment eligibility.  ASSESSMENTS	Baseline (within 14 days of enrollme nt)	Day 1	Day 8 (Rang e 6- 10)	Day 14 (Range 13-16)	Count recovery or Day 43 (Range 35-45), or Day 63 (if 5+2 given, range 55-65)	Day 1 of each Consolida tion cycle (+/- 3 days)	Day 1 of each Maintena nce cycle (+/- 3 days)	Relapse
Written consent	X							
Medical history	X							
Review of prior therapy	X							
Physical exam	X	X	X	X	X	X	Х	X
Vital signs	X	X	X	X	X	X	X	X
Weight	X	X	X	X	X	X	X	X
Height	X							
Concomitant meds	X	X	X	X	X	X	X	X
Performance status	X					X	X	X
Symptom and Toxicity Notation	X	X	X	X	Х	Х	X	X
LABORATORY EVA								
CBC w/ diff	X	X	X	X	X	Х	X	X
Complete Chemistry Panel (including magnesium and phosphate)	X	X	X	X	X	X	X	X
ALT, AST, total bili, direct bili	X	X	х	Х	Х	Х	X	Х
LDH	Х	Х	Х	Х	Х	Х	Х	Х
Uric acid	X	X	Х	X	X	Х	X	X
PT, PTT	X				_ <del></del>			
D-Dimer, fibrinogen	X							
Hepatitis B S Ag	X							
and serology								
Hepatitis C	Х							
serology								

Serum/urine	Х				
pregnancy test for					
females of child-					
bearing potential					
EKG	X				
MUGA scan or	х				
echocardiogram	_ ^				
DISEASE STATUS					
Bone marrow	X	X	X		X
biopsy/aspirate					
Skin Biopsy		X			
(Optional)					

TREATMENT

Alisertib to be administered twice daily starting on day 8 (or 9) for 7 days during induction, given days 6-12 following cytarabine during consolidation cycles (up to 4 cycles), and then resumed on count recovery for 7 days, followed by 14 days off, and continued in this manner as 21-day cycles for up to 12 cycles.

#### 13. MEASUREMENT OF EFFECT

## 13.1 Response Criteria

Complete remission (CR): Bone marrow showing less than 5% myeloblasts with normal maturation of all cell lines, an ANC of at least 1000/μL and a platelet count of 100,000/μL, absence of blast in peripheral blood, absence of identifiable leukemic cells in the bone marrow, existing extramedullary disease. If possible, at least one bone marrow biopsy should be performed to confirm CR.

Complete Remission with Incomplete Blood Count Recovery (CRi): Same as for CR but without achievement of ANC at least 1000/uL (CRi) and/or platelet count of 100,000/uL (CRp).

**Partial Remission:** All hematologic criteria of CR are fulfilled, and a decrease of bone marrow blast percentage to 5 to 25 percent; and decrease of pretreatment bone marrow blast percentage by at least 50 Percent.

**Morphologic Leukemia Free State:** Bone marrow blasts <5 percent; absence of blasts with Auer rods; absence of extramedullary disease; no hematologic recovery required

Resistant Disease: Failure to achieve CR or CRi.

**Recurrence/Morphologic Relapse**: Reappearance of leukemic blasts in the peripheral blood or > 5% blasts in the bone marrow not attributable to any other cause (e.g. bone marrow regeneration

after consolidation therapy). The appearance of new dysplastic changes should be considered

relapse. The reappearance or development of cytologically proven extramedullary disease indicates relapse. Molecular and/or genetic relapse is characterized by reappearance of a cytogenetic or molecular abnormality.

#### 14. STATISTICAL CONSIDERATIONS

This is a phase II, two-stage, single center, to assess the efficacy of alisertib in combination 7+3 induction chemotherapy in the adult higher risk AML population. Higher risk AML patients are those that (a) are at least 18 years of age with a poor risk karyotype and/or secondary AML, or (b) at least 65 years of age with AML.

The primary endpoint of this study is the rate of complete remission (CR) or complete remission with incomplete count recovery (CRi) in higher risk patients receiving alisertib in combination with 7+3 induction chemotherapy. The CR+CRi rate will be compared to the historical rates seen in this population with 7+3 induction alone. Secondary endpoints include: 1-year overall survival (OS), relapse free survival (RFS), remission duration, and toxicity for patients receiving alisertib in combination with conventional cytotoxic chemotherapy.

# 14.1 Sample Size, Accrual Rate, and Study Duration

A total of 39 evaluable patients will be enrolled based on the Simon two-stage design assuming a null CR rate of 0.45, a CR+CRi rate of 0.70 for alisertib in combination 7+3 induction chemotherapy, a 0.05 significance level, and 90% power. The first stage will accrue 13 patients; if more than 6 CR+CRi's are observed during the first stage, the trial will continue onto the second stage accruing 26 more patients. If more than 22 CR+CRi's are observed out of 39 then alisertib in combination 7+3 induction chemotherapy will be considered effective. Under this design, the probability of stopping after the first stage is 0.64. Enrollment for the first stage assessment will be held before enrolling the first patient to the second stage.

Patients removed due to presence of favorable cytogenetics prior to day 8 would be considered to be inevaluable and will be replaced. In addition, patients who receive less than half of their total alisertib dose during induction would be considered to be inevaluable and will be replaced. We anticipate that approximately 3 eligible adults per month will be accrued to this MGH/DFCI for an approximate total accrual of 39 evaluable adult high risk AML patients over 13 months.

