## 1.2 Primary Objectives

• To determine the rates of complete remission (CR), complete remission with incomplete count recovery (CRi) in higher risk patients receiving alisertib in combination 7+3 induction chemotherapy, and to assess whether this is higher than the historical rates seen in this population with 7+3 induction alone.

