## 2.2 Study Disease: Acute Myeloid Leukemia (AML)

AML is characterized by an arrest in differentiation and uncontrolled proliferation of myeloid precursors in the bone marrow. This underlying process frequently leads to hematopoietic insufficiency, and when undifferentiated cells escape the marrow, to significant leukocytosis, with often devastating and life-threatening sequelae. Unfortunately, successful treatment of AML remains a difficult challenge. Although the majority of adults under age 60 with de novo AML achieve a complete remission (CR) with traditional anthracycline and cytarabine based induction regimens, the long-term survival rates continue to be poor at approximately 30-40%. [60, 61] Remission rates and prognosis are significantly poorer for patients with high-risk AML, which includes older patients, those with poor-risk cytogenetic features, and those whose disease has arisen from myelodysplastic syndromes (MDS), myeloproliferative disorders (MPD), as well as those with secondary AML from environmental exposures or prior chemotherapy. In such cases, a remission is achieved in less than 40% of cases, with very poor long-term survival rates of less than 10%.[61, 62]

Anthracyclines and cytarabine have been the primary agents used for AML induction therapy for more than two decades. Early Cancer and Leukemia Group B (CALG-B) studies established the utility of these agents in induction regimens.[63] CALGB-7421 later demonstrated that induction with 7 days of cytarabine and 3 days of anthracycline (7+3) was superior to 5 days of cytarabine and 2 days of anthracycline (5+2).[64] Increasing the intensity of the regimen by extending the infusion of cytarabine to 10 days was also investigated, and was shown to have no impact in complete remission rate. Since that time, 7+3 has been extensively used as first line induction

Protocol Version Date: 5/18/2017

regimens in AML, although outcomes continue be frequently inadequate and poor, especially in older patients and those with high risk AML.[61]

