# 14.2 Statistical Design/Endpoints

## **Primary Endpoint**

The primary endpoint of this study is the proportion of patients who achieve a CR or a CRi (defined in section 13.1) compared to the historical rate of 0.45. It is hypothesized that the CR+CRi rate for alisertib in combination 7+3 induction chemotherapy will be 0.70. A one-sided single proportion test will be used to test the hypothesis that the remission rate of alisertib in 7+3 chemotherapy is greater than the 7+3 historical rate.

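### Does the unsourced historical rate of 0.45, set beside the below-40% remission rate in section 2.2, undermine the primary comparison?

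*Combined protocol and SAP*

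**What the plan says.** Section 14.1 sets up a Simon two-stage design "assuming a null CR rate of 0.45, a CR+CRi rate of 0.70 for alisertib in combination 7+3 induction chemotherapy", at a 0.05 level with 90% power. The first stage has 13 patients and the trial continues if more than 6 respond. The final rule reads: "If more than 22 CR+CRi's are observed out of 39 then alisertib in combination 7+3 induction chemotherapy will be considered effective". The stated probability of stopping early is 0.64.

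Section 14.2 defines the primary endpoint as "the proportion of patients who achieve a CR or a CRi (defined in section 13.1) compared to the historical rate of 0.45". Section 14 says "The CR+CRi rate will be compared to the historical rates seen in this population with 7+3 induction alone", and section 1.2 gives the same aim. None of these sections cites a source for 0.45.

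The background, section 2.2, says: "Remission rates and prognosis are significantly poorer for patients with high-risk AML, which includes older patients, those with poor-risk cytogenetic features", and goes on to include disease arising from earlier myeloid disorders and secondary AML. It then states, with citations: "In such cases, a remission is achieved in less than 40% of cases". For the trial itself, section 14 says: "Higher risk AML patients are those that (a) are at least 18 years of age with a poor risk karyotype and/or secondary AML", or anyone aged 65 or over with AML.

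**The concern.** With no concurrent control, the historical rate is the whole comparison. Three things look wrong about it.

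- It has no source.
- The only cited remission rate for high-risk AML in the protocol is lower, the risk categories are nearly the same, and nothing explains the step from below 0.40 to 0.45.
- Section 14.1 labels 0.45 a CR rate, while the alternative, both cut-offs and section 14.2 count CR plus CRi.

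Section 14.2 also plans a confidence interval for overall and relapse-free survival but only a test for remission, so the planned output would not itself show which historical rates the data exclude. At stake is the verdict for counts just under the cut-off, where a regimen could be declared not effective although it beat the protocol's own background rate. If 0.45 were a CR-only rate, the error would run the other way, towards false positives.

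**Working it through.** **Inputs.** From section 14.1: 13 patients then 26 more, continue if more than 6 of 13, effective if more than 22 of 39, rates 0.45 and 0.70. From section 2.2: an upper bound of 0.40. From section 2.1.4.2: phase I remissions of 12 CR and 2 CRp.

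**Formula.** The chance of passing stage 1 and finishing with at least k remissions at true rate p is

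R(k, p) = sum over x = 7 to 13 of P[Bin(13, p) = x] × P[Bin(26, p) ≥ k − x].

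**1. The plan's own figures.**

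- Early stopping at 0.45: P[Bin(13, 0.45) ≤ 6] = 0.6437 (stated 0.64).
- Alpha: R(23, 0.45) = 0.0468 (limit 0.05).
- Power: R(23, 0.70) = 0.9054 (stated 90%).

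The design reproduces when 0.45 is taken as a CR+CRi rate.

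**2. The same rule if the historical rate is 0.40.**

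| At least k of 39 | R(k, 0.40) | R(k, 0.45) | R(k, 0.70) |
|---|---|---|---|
| 20 | 0.0643 | 0.1745 | 0.9359 |
| 21 | 0.0391 | 0.1236 | 0.9324 |
| 22 | 0.0215 | 0.0799 | 0.9238 |
| 23 (plan) | 0.0106 | 0.0468 | 0.9054 |

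Against 0.40 the 0.05 level is already held at 21, so 21 and 22 are the counts where the choice of null matters. Keeping 23 costs 0.9324 − 0.9054 = 0.0270 of power at 0.70. That is also the probability of a final count of 21 or 22 at 0.70. At assumed true rates of 0.65 and 0.60 it is 0.079 and 0.142.

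**3. How firm is the change of verdict?** One-sided p-values against 0.40:

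| Count | Two-stage exact | Normal approximation | Single-stage exact |
|---|---|---|---|
| 21/39 | 0.0391 | 0.0388 | 0.0559 |
| 22/39 | 0.0215 | 0.0182 | 0.0280 |

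Only 22 beats 0.40 under every method; 21 depends on which is used.

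**4. Can 0.45 and below 0.40 both be right?** Section 2.2 introduces CR for younger adults and then speaks of remission, so CR is a natural reading there. Take the phase I split as an assumption: 12 of 14 remissions were CR. A CR+CRi rate of 0.45 then corresponds to a CR rate of 0.45 × 12/14 = 0.386, which is below 0.40. In the other direction, a CR bound of 0.40 corresponds to 0.40 × 14/12 = 0.467 for CR+CRi, which is above 0.45.

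The populations also differ. Sections 3.1 and 3.2 require fitness for induction, ECOG 0–2 and an ejection fraction above 50%, and exclude favorable cytogenetics. Section 14.1 replaces patients who receive less than half of their induction alisertib, which starts on day 8 or 9, so very early deaths leave the denominator. The fitness requirements and the replacement rule plausibly raise the expected rate above a general background figure.

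**5. The interval.** Solving R(k, p) = 0.05 for p gives a two-stage lower limit (the lower end of a 90% interval) of 0.409 at 21, 0.430 at 22 and 0.453 at 23. It needs only the final count and the stage rule.

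**The case for a change.** The strongest case for acting is that the sole comparator should be traceable, and that a reader cannot tell from the protocol whether 0.45 is CR or CR+CRi. If it were CR-only, the phase I split would put the CR+CRi null at 0.45 × 14/12 = 0.525, where the stated rule has a false-positive probability of 0.223. That would matter. The reading is hard to sustain, though: section 14.2 attaches 0.45 directly to the proportion with CR or CRi, and section 14 compares the CR+CRi rate with history. The 0.525 itself rests on 14 remissions among 16 patients given the combination rather than 7+3 alone, 11 of them high risk.

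A second argument is that a null of 0.40 would allow a smaller trial. A Simon design for 0.40 against 0.70 at the same error rates needs 24 patients (more than 4 of 10, then more than 13 of 24). But designs with 33 or 35 patients already meet 0.45 against 0.70, so the null accounts for only 33 − 24 = 9 to 35 − 24 = 11 of the 15-patient difference from 39. A stricter benchmark in an uncontrolled trial is a reasonable thing to buy with them.

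What stands: the source is missing, the label in section 14.1 is loose, and no sentence links 0.45 to section 2.2.

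**Conclusion.** The observation is accurate but calls for no change. It comes down to a missing citation and a clerical label. Section 14.2 resolves the label, and the decision rule gives one verdict for every count. Against 0.45 that rule does what section 14.1 claims (alpha 0.0468, power 0.905). If the background figure is the better guide, the rule errs on the safe side: alpha falls to 0.0106 at 0.40, while power at 0.70 does not depend on the null. The price is a count of 21 or 22, with probability 0.027 at the design alternative and 0.079 to 0.142 at assumed rates of 0.65 to 0.60. An interval would help a reader judge the result against either rate, and an analyst can supply it from the count.

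This rests on reading 0.45 as a CR+CRi rate, as section 14.2 does. The reconciliation with section 2.2 is plausible but not shown: it assumes that section 2.2 means CR and that the phase I split carries over. The conclusion does not depend on it, because a historical rate below 0.45 only makes the stated test stricter.
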